2 OBJECTIVES

The objective of the study is to compare the rate of tear evaporation, measured with a novel evaporimeter, before and after DAILIES TOTAL1 and Biotrue ONEday CLs are worn in symptomatic and asymptomatic contact lens wearers.

The primary outcome variable for this study are the slopes calculated from the change in relative humidity over time.

Other variables of interest include:

- Contact lens dry eye questionnaire-8 (CLDEQ-8) score
- Comfort (subjective rating)
- Dryness (subjective rating)
- Non-invasive break up time
- Lipid layer thickness (Tearscope, LipiView II)
- Ocular surface area (mm²)
- Volume inside the goggle (cm³)

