3 HYPOTHESIS

The study hypothesis is that there will be a higher rate of tear evaporation with CL wear compared to when CLs are not worn.

There will also be a significant difference in the rate of tear evaporation of DAILIES TOTAL1 (DT1) and Biotrue ONEday (BOD) after a minimum of 6 hours of CL wear.

There will also be a higher rate of tear evaporation in symptomatic contact lens wearers compared to asymptomatic lens wearers.

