4.1.2 RANDOMIZATION

A randomization schedule will be generated using a web-based program: (www.randomization.com). Participants will be randomized to the type of contact lens to be worn in each eye at Visit 2. A separate randomization will be generated for symptomatic and asymptomatic participants. The final study randomization schedule will be generated by CORE's Database Administrator, and provided to the research assistants for the study. Study investigators will remain masked to the randomization schedule until the interim data analysis. Study investigators will be granted access to the randomization schedule for the first 10 symptomatic and 10 asymptomatic participants in order to conduct the interim data analysis. Following

calculation of the sample size required to complete the study, study investigators will remain masked to the remainder of the randomization schedule until the study is completed and the database is locked.

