4.2 STUDY POPULATION

4.2.1 SAMPLE SIZE CALCULATION

Because this is a pilot study, a sample size calculation has not been completed. An interim data analysis will be undertaken after 20 participants (10 symptomatic and 10 asymptomatic) have completed the study. The results of the interim data analysis will be used to calculate a sample size using G*Power.

A p-value of < 0.05 will be considered statistically significant.

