10 STATISTICAL ANALYSIS AND DATA MANAGEMENT

10.1 STATISTICAL ANALYSIS

All data will be analyzed by CORE at the University of Waterloo on unmasked data using Microsoft Excel and statistical analysis software such as GraphPad and SPSS. Interim data analysis will be conducted after 10 symptomatic and 10 asymptomatic participants have completed the study to determine the optimal time period over which to calculate the slope. The results of the interim data analysis will also be used to calculate the sample size.

Descriptive statistics will be provided on information regarding baseline variables (age, sex, contact lens refractive error distribution, etc.). Data may be evaluated for individual groups

(asymptomatic versus symptomatic) and when both groups are combined. Data will be tested for normality of distribution using Shapiro-Wilk tests. A p -value of < 0.05 will be considered statistically significant. Additional analysis may be conducted.

Table 4 lists the primary outcome variables and anticipated statistical procedures.

Table 4: Outcome variables and anticipated statistical procedures

| Variable | Analysis | Statistical test |
|--------------------------------------------------------------------------------------------------------------------------------------------------------------|--------------------------------------------------------------------------------------------------------------------|--------------------------------------------------------------------------------------------------------------------|
| Tear evaporation rate | Change in relative humidity over time | Slope |
| Tear evaporation rate/Time | Effect of lens type | RMANOVA Mauchly's test of sphericity Greenhouse-Geisser p values Tukey HSD post hoc Paired t -test |
| Tear evaporation rate/ Subjective ratings/Non- invasive breakup time/Lp d ayer thickness (Lp View II - continuous)/Area of the ocular surface | Relationship between tear evaporation rate and subjective comfort and dryness/other tear film assessments | Pearson correlation – r |
| Tear evaporation rate/ Lp d ayer thickness (Tearscope - ordinal)/ Volume of the goggle | Relationship between tear evaporation rate and lpdayer thickness | Spearman correlation – ρ |

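### No lead comparison is named for tests in three overlapping participant sets at p<0.05, and symptom group is missing from the planned model: if all are run, chance findings reach about 12% for the lens question and about 26% across the three hypotheses

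*Combined protocol and SAP*

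**What the plan says.** - **Hypotheses (section 3).** Three are stated, in no order of priority. Hypothesis 1: "there will be a higher rate of tear evaporation with CL wear compared to when CLs are not worn". Hypothesis 2: "There will also be a significant difference in the rate of tear evaporation of DAILIES TOTAL1 (DT1) and Biotrue ONEday (BOD"), set after at least 6 hours of wear. Hypothesis 3: "higher rate of tear evaporation in symptomatic contact lens wearers compared to asymptomatic lens wearers".
- **Primary outcome (section 2).** "The primary outcome variable for this study are the slopes calculated from the change in relative humidity over time". This fixes a variable, but not a comparison, a session or an analysis set.
- **Analysis sets (section 10.1).** Data may be evaluated for the individual groups ("asymptomatic versus symptomatic) and when both groups are combined"). That makes three sets: symptomatic, asymptomatic and pooled. The section also leaves room for further analyses.
- **Threshold (sections 4.2.1 and 10.1).** "A p-value of < 0.05 will be considered statistically significant". Sidedness is not given.
- **Planned tests (Table 4).** For the effect of lens type: repeated-measures ANOVA (RMANOVA) with Tukey HSD post hoc, and a paired t-test. The rest are correlations. The table has no symptom-group factor, between-group test or lens-by-group interaction.
- **Randomisation (section 4.1.2).** "A separate randomization will be generated for symptomatic and asymptomatic participants".

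**The concern.** There are two problems.

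First, a lens or wear effect can reach significance in the symptomatic group, in the asymptomatic group or in the pooled sample, and nothing says in advance which result carries the claim. Each test has a 5% error rate, but the claim that an effect was found does not.

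Second, symptom group is built into the design and into hypothesis 3, yet the planned model leaves it out. The only described way of looking at symptom groups is to repeat the analysis within each. Two within-group p-values do not show whether the lens effect differs between the groups. If one is below 0.05 and the other is not, a reader may see a lens-by-symptom difference when the underlying effects are the same.

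**Working it through.** The plan gives no power, effect size, standard deviation or overall error rate to reproduce. Its only figure is 0.05 per test.

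**Inputs**
- Alpha 0.05 per test (4.2.1, 10.1); two-sided is an assumption.
- Three analysis sets (10.1).
- Hypotheses 1 and 2 can be tested in all three sets. Hypothesis 3 compares the groups, so it can be tested only in the whole sample. Total: 2 × 3 + 1 = 7 tests.
- 10 per group is the minimum completing. Up to 50 may be randomised (4.2.2), taken here as 25 per group (assumption).
- Standardised paired lens effect d_z: not in the documents. A range of 0.3 to 1.0 is assumed.

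**Step 1: ceiling if the tests were independent.** 1 − (1 − 0.05)^k gives 14.3% for k = 3, 26.5% for k = 6 and 30.2% for k = 7. These are too high, because the pooled test contains the data of both group tests.

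**Step 2: allow for the overlap.** Simulation with all nulls true and two-sided t-tests (200,000 runs). The pairs show the wear and lens contrasts uncorrelated / correlated 0.5.

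| Tests run | 10 per group | 25 per group |
|---|---|---|
| Lens comparison, three sets | 11.7% / 11.8% | 11.6% / 11.6% |
| Hypotheses 1 and 2, three sets (6 tests) | 22.1% / 20.8% | 22.0% / 20.5% |
| The same plus hypothesis 3 once (7 tests) | 26.0% / 24.8% | 25.8% / 24.4% |
| Three hypotheses, combined set only | 14.2% / 13.5% | 14.3% / 13.6% |

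Hand check of the third row, uncorrelated case: 1 − (1 − 0.117)² × 0.95 = 1 − 0.780 × 0.95 = 0.259.

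**Step 3: discordant groups under an identical true lens effect.** With per-group power p, the chance that exactly one group is significant is 2p(1 − p). Simulated values (50,000 runs):

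| d_z | Power, n=10 | Exactly one, n=10 | Power, n=25 | Exactly one, n=25 |
|---|---|---|---|---|
| 0.3 | 13.6% | 23.5% | 30.0% | 42.5% |
| 0.5 | 29.4% | 41.6% | 66.4% | 44.0% |
| 0.66 | 46.2% | 49.9% | 88.4% | 20.3% |
| 0.8 | 61.9% | 47.2% | 97.0% | 5.9% |
| 1.0 | 80.4% | 31.4% | 99.8% | 0.4% |

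At 25 per group, power passes 50% between d_z 0.3 and 0.5. There the formula reaches its maximum, 2 × 0.5 × 0.5 = 50%. Over the assumed range the chance is therefore 23–50% at 10 per group, and from under 1% to 50% at 25 per group. A direct test of the difference in lens effect between groups rejected in 4.8–5.2% of runs at every d_z and group size shown.

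**Step 4: text against text.** Section 3 states a symptom-group hypothesis and 4.1.2 randomises by symptom group. Table 4 lists no test that could address that hypothesis.

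**The case against.** - **The study is a pilot, and the group analyses are optional.** Whether three distinct questions in a pilot need joint error control is a matter of judgement, and the 12% and 26% apply only if the analyses are all run. This stands as a limit on priority. It does not remove the point: section 3 predicts a significant difference and 4.2.1 sets a threshold for declaring one. Optional analyses widen the choice of result to report.
- **Some structure exists.** Tukey HSD controls error among post hoc comparisons inside each RMANOVA, and hypothesis 2 is tied to at least 6 hours of wear. Both are true. Neither covers repetition across the three sets or across the hypotheses.
- **No lens-by-symptom claim is planned.** Correct: section 3 states none. The risk lies in how separate group results would be read, so the text supports saying that they can mislead, not that they will.
- **Table 4.** A reader might infer from its lead-in ("Table 4 lists the primary outcome variables and anticipated statistical procedures") that every listed variable is primary. The table's own caption drops that word and section 2 names one primary variable, so this is a wording slip.
- **A fixed testing sequence would be costly.** Letting a non-significant lens result block the other two stated hypotheses is a debatable trade in a pilot. This objection is accepted, and the fix avoids it.

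**Conclusion.** The concern holds in a limited form. With two-sided tests, no true effects and all permitted analyses run, the chance of at least one significant result is about 12% for the lens comparison in three sets. It is about 26% across the three hypotheses when hypothesis 3 is tested once (about 25% if the wear and lens contrasts are moderately correlated).

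A reader might infer about 30%. That figure needs seven independent tests, which these are not, or hypothesis 3 tested separately at three sessions. Hypothesis 3 names no session, but nothing in the protocol plans three tests of it.

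A reader might also infer that significance in one group only would usually be chance. The documents do not support that: the discordance rates assume equal true effects, and they run from under 1% to 50% depending on an effect size that the plan does not give. What is supported is that separate group p-values are an unreliable way to look for a difference between groups, and that the direct test keeps its 5% error.

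This is worth correcting, at modest priority given the pilot status.

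**What to change.** In section 10.1:

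1. Name DT1 versus BOD after at least 6 hours of wear, both groups combined, as the lead test at two-sided 0.05. It is the randomised comparison, and section 3 already ties it to a wear time. Section 3 lists the wear effect first, so the sponsor could choose that instead; what matters is naming one.
2. Add symptom group as a between-participant factor in the RMANOVA. Its main effect tests hypothesis 3, once. The lens-by-group interaction at the 6-hour session compares the DT1-minus-BOD differences between the two groups.
3. Replace within-group significance tests of the lens effect with per-group estimates and 95% confidence intervals.
4. Report hypotheses 1 and 3 as secondary, not conditional on the lens result.
5. Label the Table 4 correlations exploratory, and drop the word primary from the sentence that introduces the table.

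The lead claim then carries 5% error. The three hypotheses taken together in the combined set still carry about 14%, which is acceptable once only one of them leads.

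Cost: a few sentences, with no added participants, visits or measurements. There will be fewer nominally significant subgroup results, and the interaction test will have low power at these group sizes, so its confidence interval should be read rather than its p-value alone.

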4 MATERIALS AND METHODS

4.1 STUDY DESIGN

4.1.1 OVERALL DESIGN

[figure not shown]
This study is a prospective, double-masked (investigator and participant), contralateral, non-dispensing study. Each participant will be randomized to wear DT1 in one eye and BOD in the fellow eye. Both lenses will be worn on a daily wear basis. This study will involve 3 scheduled visits over 2 days.

Visit 1: Screening and contact lens fitting visit

Visit 2: Baseline dispensing visit with BOD and DT1 lenses (morning visit)

Visit 3: Follow up visit with BOD and DT1 lenses (afternoon visit)

Visit 2 (baseline visit) and Visit 3 (follow up visit) will be conducted on the same day. There will be 5.5 hours \pm 30 minutes between Visit 2 and Visit 3, during which time participants are not required to remain at the School of Optometry & Vision Science.

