4.2.2 NUMBER OF PARTICIPANTS

Up to 50 participants will be screened using CORE records and advertising approved by the UW Office of Research Ethics. Up to 50 participants will be dispensed/randomized with study products, with a target of at least 10 symptomatic and 10 asymptomatic participants completing the study. Informed consent will be obtained for all participants prior to their enrolment in the study.

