8 DISCONTINUATION FROM THE STUDY

Participants may be discontinued at the discretion of the investigator or sponsor in consideration of participant safety or protocol compliance, or at discretion of the participant. Participants discontinued from a study will be reimbursed \$20 per hour for their active involvement in the study (including the initial screening visit). Upon discontinuing, a participant will be offered the option of their data being withdrawn from future statistical analysis. The following is a list of possible reasons for discontinuation from the study:

- Screening failure: Participants will be discontinued if they do not meet the inclusion and exclusion criteria outlined in section 4.2.3.
- Unacceptable performance with products to be used in study: Participants may be discontinued if they are unable to achieve acceptable comfort and /or vision with the study products.
- Positive slit lamp finding: Participants may be permanently discontinued from the study depending on the severity of the condition and on the judgement of the investigator.
- Adverse event: If a participant experiences an adverse event during the study they may be discontinued based on the clinical judgement of the investigator.
- Symptoms: If the participant has persistent symptoms they may be discontinued based on the clinical judgement of the investigator.
- Disinterest, relocation or illness: The participant may choose to discontinue due to reasons within or beyond their control.
- Violation of protocol or non-compliance: The participant will be discontinued if they are unable or unwilling to follow the protocol specified visit schedules and/or study procedures.
- Instillation of topical ocular medication: The participant will be discontinued if they elect to use a topical ocular medication during the study unless that topical ocular medication is prescribed for a limited duration (less than two weeks) to treat a transient condition; in

this case the participant may remain an active participant (at the discretion of the investigator) after stopping topical ocular medication following resolution of the ocular condition).

- Lost to follow-up: The participant will be discontinued if they cannot be contacted and do not return for a final exit visit, and if the investigator has made a reasonable effort to contact the participant for a final study visit.

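### The repeated-measures ANOVA in Table 4 uses complete cases only, so a participant without Visit 3 contributes nothing to it; the effect is probably small, and a correctly specified mixed model removes it

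*Combined protocol and SAP*

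**What the plan says.** Section 10.1, Table 4, lists "RMANOVA Mauchly's test of sphericity Greenhouse-Geisser p values" for the effect of lens type on tear evaporation rate over time, followed in the same cell by Tukey post hoc tests and a paired t-test. Correlations appear in later rows. The analysis will use "statistical analysis software such as GraphPad and SPSS". The section gives no missing-data rule and defines no analysis set.

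The design is contralateral: "Each participant will be randomized to wear DT1 in one eye and BOD in the fellow eye". Evaporimetry is done in four sessions. Section 4.4.3 (Visit 2) has two without lenses and one after the lenses have settled. Section 4.4.4 (Visit 3, same day) has one after at least 6 hours of wear.

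The protocol foresees incomplete participants. Section 8 says: "Participants may be discontinued if they are unable to achieve acceptable comfort and /or vision with the study products". It lets a participant who discontinues choose whether to withdraw their data, so data not withdrawn are presumably meant to remain usable. Section 13.4.2 gives a missed measurement within a session as an example of a minor deviation.

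Numbers are counted in completers. Section 4.2.2 allows up to 50 to be randomized, "with a target of at least 10 symptomatic and 10 asymptomatic participants completing the study". Section 4.2.1 says: "An interim data analysis will be undertaken after 20 participants (10 symptomatic and 10 asymptomatic) have completed the study".

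**The concern.** A classical RMANOVA deletes a participant from every cell if any one cell is empty. Someone who goes home with the lenses in and does not return for Visit 3 has already supplied two no-lens sessions and one early lens session in both eyes. None of these readings enters the test. The same happens to a completer with one failed session.

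Two things are at stake. The first is precision, in a study that may be analysed with about 20 people. The second is who is represented. The first hypothesis in section 3 (lens wear against no lens) can be informed by Visit 2 alone, yet under RMANOVA it would rest only on people who kept both lenses in until the afternoon. Because the plan is silent and section 10.1 says the analysis uses unmasked data, the handling of incomplete participants is left to a software default or to a choice made with lens identity known.

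**Working it through.** The documents state no dropout rate, variance or power (section 4.2.1: "Because this is a pilot study, a sample size calculation has not been completed"), so there is no planned figure to reproduce. Stopping rates and variance shares below are assumptions.

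**1. Layout.** 4 sessions × 2 eyes = 8 readings per participant, each reading being the average described in section 4.5.16. A participant who stops after Visit 2 has 3 × 2 = 6 of 8. RMANOVA over all four sessions uses 0; a mixed model uses 6.

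**2. Mechanical check.** Data were simulated for 22 participants, 2 of them without Visit 3: 20 × 8 + 2 × 6 = 172 readings. The classical routine rejected the data as unbalanced. It ran only after both participants were removed (20 participants, 160 readings, 12 valid readings discarded). The mixed model ran on all 22 participants and 172 readings.

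**3. Readings discarded.** With n starters and k stoppers, the loss is 6k of 8(n − k) + 6k. For n = 20:
- k = 1: 6 of 158 (3.8%)
- k = 2: 12 of 156 (7.7%)
- k = 4: 24 of 152 (15.8%)

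**4. Precision, Visit 2 contrasts.** This covers lens against no lens at Visit 2, and DT1 against BOD at 15 minutes. Complete cases number n − k, but all n have Visit 2 data. The standard error (SE) ratio is therefore √(n/(n − k)) = 1/√(1 − d), where d = k/n is the share stopping:
- d = 5%: 1/√0.95 = 1.026
- d = 10%: 1/√0.90 = 1.054
- d = 20%: 1/√0.80 = 1.118

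**5. Precision, DT1 against BOD at 6 hours or more.** A stopper has no Visit 3 reading in either eye and helps only through correlation with the earlier between-eye differences. Take total variance 1 with shares for participant, eye and participant-by-session, the remainder w being residual. The between-eye differences then correlate across sessions at r = eye/(eye + w). Three earlier sessions predict the fourth with R² = 3r²/(1 + 2r). The SE ratio is 1/√(1 − R²d), with variances treated as known.

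| Shares (participant / eye / session) | w | r | R² | d = 5% | d = 10% | d = 20% |
|---|---|---|---|---|---|---|
| 0.3 / 0.1 / 0.1 | 0.5 | 0.167 | 0.0625 | +0.2% | +0.3% | +0.6% |
| 0.4 / 0.2 / 0.2 | 0.2 | 0.500 | 0.375 | +1.0% | +1.9% | +4.0% |
| 0.3 / 0.4 / 0.1 | 0.2 | 0.667 | 0.571 | +1.5% | +3.0% | +6.3% |

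**6. Which mixed model.** One goggle reads both eyes at once (sections 1 and 4.5.16), so the two eyes share session-level error. With participant-by-session share s, the session mean square under no effect has expectation w + 2s. A model with only participant and eye-within-participant random effects tests it, in balanced data, against a pooled residual with expectation w + s. The F ratio is inflated by (w + 2s)/(w + s): 0.7/0.6 = 1.17, 0.6/0.4 = 1.50 and 0.4/0.3 = 1.33 for the three rows above. In simulated complete data with no session effect (20 participants, nominal 5%), that model rejected in 7.9%, 15.5% and 11.6% of runs, against about 4.9% for RMANOVA. The session effect carries the lens-against-no-lens hypothesis, so the participant-by-session term is essential.

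**The case against.** The strongest reply is that little will be lost. Visits 2 and 3 are 5.5 hours ± 30 minutes apart on one day (section 4.1.1). Entrants already wear soft lenses at least 8 hours a day on at least 4 days a week, and must find both study lenses acceptable in fit and comfort (section 4.2.3). The comfort-and-vision rule in section 8 could also be applied at the Visit 1 fitting, before any analysed evaporimetry. Each reading averages three repeats, so one bad measurement need not empty a cell. Table 4 calls its procedures anticipated and does not say which sessions enter the RMANOVA. All of this stands, and it limits the size of the point. It does not supply a missing-data rule.

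Four stronger readings are tempting and are not supported:
- **That early stoppers vanish from the whole analysis.** The paired t-test in the same cell and the correlations can still use their Visit 2 readings. The loss is specific to the RMANOVA.
- **That the planned 20 shrinks.** Independent loss of 1%, 2% or 5% per session gives 1 − (1 − p)⁴ = 3.9%, 7.8% or 18.5%, or 0.8, 1.6 or 3.7 of 20. But the 20 are completers, so early stoppers come on top of them, and only a failed session in a completer could reduce the number. The mechanism described is also one loss at Visit 3, not four independent losses.
- **That the selection is known to bias the symptom comparison.** Comfort-related stopping may plausibly differ between symptomatic and asymptomatic wearers, but the documents give no figure by which to size it.
- **That any mixed model is a free improvement.** Step 6 shows that one without the participant-by-session term would replace a valid session test with an anticonservative one.

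**Conclusion.** The point holds in limited form. As planned, the RMANOVA is complete-case, and nothing in the documents says how incomplete participants are handled. In any layout that includes Visit 3, a participant who stops after Visit 2 has 6 of 8 readings and none is used; a completer with one missing session is dropped in the same way.

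The gain from keeping them lies mainly in the Visit 2 contrasts. For the two lenses at 6 hours it is small, reaching 6.3% only if 20% stop and between-eye differences are strongly correlated across sessions. Actual stopping is probably towards the low end of the assumed 5% to 20%. The change is worth making because it is cheap, not because the planned test is invalid: with complete data the RMANOVA is sound, and a mixed model with matching error terms gives essentially the same lens and session tests.

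**What to change.** In Table 4, replace RMANOVA as the main analysis of tear evaporation rate with a linear mixed model on all available sessions, and state that every participant with at least one valid session is included unless their data have been withdrawn under section 8. Specify:
- **Fixed effects:** lens, session, lens-by-session, and symptom group with its interactions of interest. Without symptom group the third hypothesis in section 3 cannot be tested from the model.
- **Random effects:** participant, eye within participant, and participant-by-session.
- **Degrees of freedom:** Kenward-Roger or Satterthwaite.
- **Hypotheses:** pre-specified contrasts for lens against no lens, DT1 against BOD at 6 hours or more, and symptomatic against asymptomatic.
- **Sensitivity analysis:** the complete-case RMANOVA as now planned, with the number of participants excluded from it and the reasons.

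The cost is SAP wording and slightly more analysis work; a mixed model can be run in SPSS, which section 10.1 already names. The model assumes that data are missing at random given the readings observed. Stopping because one lens is uncomfortable could strain that assumption, so the report should give stopping reasons by symptom group.
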